## 5.2 Treatment Regimen

Subjects will apply the study drug topically to NL lesions twice daily. Treatment will take place from Day 0 to Week 12.

## 5.3 Preparation and Administration of Study Drug

The study drug will be supplied by Incyte to the Mayo Clinic Pharmacy, attn. [REDACTED], [REDACTED]. The study drug will be stored in the Mayo Clinic Pharmacy. The study drug will be labelled in the Mayo Clinic Pharmacy and will be dispensed to the subjects. The subjects will be given the appropriate amount of topical cream to apply to the disease. Instructions on proper use will be provided to each subject.

## 5.4 Subject Compliance Monitoring

Compliance will be assessed through direct questioning of subjects as well as through drug use diaries. Drug compliance is defined as 80-100% as the ratio between actual and prescribed applications between individual study visits. The drug tubes will be weighed, and weight will be documented at each visit to determine usage.

## 5.5 Prior and Concomitant Therapy

Individuals on stable doses of medications for chronic illnesses will be allowed. Individuals on immunosuppressive agents for NL will not be allowed; however, individuals on stable doses of immunosuppressant for other conditions will be allowed if deemed to be safe by the treating physicians. Additional exclusionary drugs are included in Table-1.

Individuals using Ruxolitinib cream should use topical broad spectrum sunscreens with a minimum of SPF30, avoid excess sunlight, and wear sun protective clothing. Sunscreens should not be applied onto treated NL lesions within 4 hours of the planned use of study drug and within one hour thereafter.

## 5.6 Packaging

The drug will be packaged in 15 gram single tubes and bubble wrapped for shipment. The entire quantity needed for the study will be provided in one shipment. The study drug tubes will be labeled with a diaper label that fully surrounds the tube. All applicable US FDA required text will be included on the label.

## 5.7 Receiving, Storage, Dispensing and Return

### 5.7.1 Receipt of Drug Supplies

The drug will be obtained or delivered from Incyte Corporation to the pharmacy at each investigative site.

Upon receipt of the study treatment supplies, an inventory must be performed and a drug receipt log filled out by the person accepting the shipment. It is important that the designated study staff counts and verifies that the shipment contains all the items noted in the shipping invoice. Any discrepancies, damaged or unusable study drug in a given shipment (active drug or comparator) will be documented in the study files. The sponsor-investigator must be notified immediately of any discrepancies, damaged or unusable products that are received.

### 5.7.2 Storage

The drug product (ruxolitinib) and placebo cream should be stored between 15°C and 30°C (59°F and 86°F). The supplies will be stored in the Mayo Clinic Pharmacy.

### 5.7.3 Dispensing of Study Drug

Regular study drug reconciliation will be performed to document drug assigned, drug dispensed, drug returns, and drug remaining. This reconciliation will be logged on the drug reconciliation form, and signed and dated by the study team.

#### **5.7.4 Return or Destruction of Study Drug**

At the completion of the study, there will be a final reconciliation of drug shipped, drug dispensed, drug returns, and drug remaining. This reconciliation will be logged on the drug reconciliation form, signed and dated. Any discrepancies noted will be documented and investigated, prior to return or destruction of unused study drug. Drug destroyed on site will be documented in the study files.

### **6 Study Procedures**

Due to COVID-19 transmission concerns, traveling patients will have the option to participate in virtual visits in lieu of in-person clinic visits at the discretion of the Principal Investigator. Laboratory studies that can be performed off-site will be permitted at the discretion of the Principal Investigator. Study drug will be given to the patient at in-person visits that will last them the appropriate time until their next in-person clinic visit. Patients residing outside of Arizona will be eligible for travel reimbursement and will give the research coordinator the receipts of purchased flights, hotel, and meals as needed. Patients will also have the option to do remote-consenting. This will be done via phone and a copy will be mailed to the patient.

#### **6.1 Visit 1**

##### Screening visit:

During this visit, we will do some tests and procedures to see if subjects are eligible to take part in this research study. The study staff will review the results of these tests and procedures. If subjects aren't eligible, the Principal Investigator will tell them why. At this visit we will:

- Ask about medical history
- Perform a physical exam, including height, weight, and “vital signs” (blood pressure, temperature, heart and breathing rates)
- Perform a chest x-ray to screen for underlying coccidioidomycosis
- Draw a blood sample
- We may take swabs to test for certain fungal and bacterial infections
- Test urine for pregnancy if female subject is able to become pregnant

If it isn't known if subject has HIV, Hepatitis B or C, blood tests will need to be done.

#### **6.2 Visit 2**

Day 0 Visit we will:

- Perform a physical exam, check vital signs and ask about side effects or health problems since last visit
- Exam skin lesions to note any changes

- Take photographs of skin lesions to document any changes
- Draw a blood sample
- Perform a skin biopsy ( 2 tissue samples will be taken)
- Dispense study drug

### **6.3 Visit 3**

Week 1 Visit we will:

- Perform a physical exam, check vital signs and ask about side effects or health problems since last visit

- Exam skin lesions to note any changes
- Take photographs of skin lesions to document any changes
- Draw a blood sample
- Dispense study drug

### **6.4 Visit 4**

Week 2 Visit we will:

- Perform a physical exam, check vital signs and ask about side effects or health problems since last visit
- Exam skin lesions to note any changes
- Take photographs of skin lesions to document any changes
- Draw a blood sample
- Dispense study drug

### **6.5 Visit 5**

Week 3 Visit we will:

- Perform a physical exam, check vital signs and ask about side effects or health problems since last visit
- Exam skin lesions to note any changes
- Take photographs of skin lesions to document any changes
- Draw a blood sample
- Dispense study drug

### **6.6 Visit 6**

Week 4 Visit we will:

- Perform a physical exam, check vital signs and ask about side effects or health problems since last visit
- Exam skin lesions to note any changes
- Take photographs of skin lesions to document any changes
- Draw a blood sample
- Perform a skin biopsy (1 tissue sample will be taken)
- Dispense study drug

## 6.7 **Visit 7**

Week 8 Visit we will:

- Perform a physical exam, check vital signs and ask about side effects or health problems since last visit
- Exam skin lesions to note any changes
- Take photographs of skin lesions to document any changes
- Draw a blood sample
- Dispense study drug

## 6.8 **Visit 8**

Week 12 Visit we will:

- Perform a physical exam, check vital signs and ask about side effects or health problems since last visit
- Exam skin lesions to note any changes
- Take photographs of skin lesions to document any changes
- Draw a blood sample

## 6.9 **Visit 9**

Week 16 Visit we will:

- Perform a physical exam, check vital signs and ask about side effects or health problems since last visit
- Exam skin lesions to note any changes
- Take photographs of skin lesions to document any changes
- Draw a blood sample.

# 7 Statistical Plan

## 7.1 Sample Size Determination

Data analysis: Due to the costs associated with a study, we propose a single armed study of 12 subjects with corollary science including RNA sequencing. This will reduce costs and provide

biomarkers predictive of response. Effect sizes will be estimated for the appropriate statistical tests that will be used for group comparisons in future studies. This will enable more accurate power and sample size estimates moving forward.

## 7.2 Statistical Methods

### Descriptive Statistics

#### Sample Size Computation and Power Analysis:

The sample size for this pilot study is set at 12 subjects for logistical and financial reasons. This is similar in size to other exploratory studies and will provide adequate data for estimation purposes for planning future studies. With 12 subjects, the study is intended to be for estimation purposes only.

#### Statistical Analysis Plan:

Data Analysis - The statistical analysis will provide descriptive summary statistics for categorical and continuous outcomes. Categorical variables will be described by their count and proportion of occurrence while continuous, normally distributed variables will be described by their mean and standard deviation; and continuous, non-normally distributed variables will be described by their median and range. The paired or unpaired Wilcoxon tests will be used to quantify differences in numerical outcomes while the Fisher's exact test and the McNemar's or Bowker's tests will be used to quantify changes in categorical variables.

If missingness occurs at random a mixed model will be utilized to assess the change in the lesion over time. A sensitivity analysis will be performed using the last observation carried forward and the results will be compared to that of the mixed-model.

Effect sizes will be estimated for the appropriate statistical tests that will be used for group comparisons in future studies. This will enable more accurate power and sample size estimates moving forward.

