### 1.1 Background

Necrobiosis lipoidica (NL) is a chronic, disfiguring, relapsing-remitting inflammatory disease primarily involving the lower extremities. NL disproportionately afflicts younger patients and is classically associated with diabetes mellitus (DM). Clinically, NL presents with atrophic yellow telangiectatic plaques that ulcerate in 30% of patients.

Although multiple therapies have been used to treat NL lesions, experience is largely anecdotal and there is paucity of data to guide effective treatment. Topical, intralesional, and systemic corticosteroids have been effective in a small number of non-DM patients; however, corticosteroids are high-risk treatment option in diabetic patients because they increase blood glucose levels and promote insulin resistance. Various non-steroidal immunosuppressants have been used, including methotrexate, tumor necrosis factor alpha inhibitors, mycophenolate mofetil, and fumaric acid esters, all with mixed success. Better treatment options with acceptable risk/benefit profile are clearly needed.

To characterize NL at the molecular level, we performed RNA sequencing to identify underlying immune mechanisms and possible therapeutic targets. We sequenced 18 representative NL tissues and 5 normal skin tissues, and identified deregulated genes enriched for immune system functions. Independent validation was performed using a Nanostring expression panel (594 immune-specific genes), demonstrating high concordance in the set of genes identified as differentially expressed by both platforms. Upregulated immunologic processes/pathways included those involved in T-helper cell induction, dendritic cell maturation, macrophage stimulation, and autoimmunity, indicating diverse immunological pathways are active in NL.

Importantly, we focused on identifying targetable “drivers” of downstream RNA expression changes. We prioritized such driver genes using by querying multiple drug databases in order to identify clinically targetable drivers. Using stringent criteria, we identified JAK1/2 and IFN $\gamma$  as key, activated drivers, and ruxolitinib as one of the most highly rated potential therapeutics in this search.

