### Psoriasis

Study INCB 18424-201: a double-blind, vehicle-controlled, increasing strength, safety, tolerability, PK, and preliminary efficacy study of ruxolitinib cream 0.5% QD (n = 6), 1.0% QD (n = 6), and 1.5% BID (n = 6) in Part 1. Efficacy (change from baseline to Day 28 in mean total lesion scores) was consistently shown for the 1.0% QD and 1.5% BID cohorts compared with vehicle. In Part 2, 1.5% BID showed a change in mean total scores for target lesions compared with Dovonex® (calcipotriene) 0.005% (n = 6) and with Diprolene® AF (betamethasone dipropionate) 0.05% (n = 5) at Day 28.

Study INCB 18424-202: an open-label, multicenter, sequential-cohort, increasing strength, safety, tolerability, PK, PD, and preliminary efficacy study of different regimens of ruxolitinib cream applied for 4 weeks (28 days) to participants based on their BSA: 2% to 7% (1.5% BID; n = 5), 8% to 13% (1.5% BID; n = 5), 14% to 20% (1.5% BID; n = 5), 14% to 20% (1.0% BID; n = 5), and 14% to 20% (1.5% QD; n = 5). The results of this study indicated that all 5 of these regimens were effective in decreasing the individual signs of lesion severity, lesion area, and the overall disease severity of psoriatic plaques.

Study INCB 18424-203: a double-blind, randomized, multicenter, parallel-group, vehicle-controlled dose-ranging study to compare the safety and efficacy of ruxolitinib cream 0.5% (n = 51), 1.0% (n = 49), or 1.5% (n = 49) QD with a vehicle cream (n = 50) when applied for 12 weeks (84 days). Overall, 199 participants were enrolled of which 161 (80.9%) completed the Day 84 visit. Within each active treatment group, the mean scores for the individual and total psoriasis lesion assessments, the PASI, and the PGA, as well as the mean treatable percent BSA decreased from baseline to each subsequent assessment, which indicated an overall lessening of disease severity.

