### **3.2 Number of Subjects**

12 subjects will be enrolled in this study.

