### **3.4 Primary Study Endpoints**

Change in NL score (0-12) of the index treatment lesions (weeks 0 and 12).

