### 4.4 Early Withdrawal of Subjects

#### 4.4.1 When and How to Withdraw Subjects

- Subject safety issues
- Failure of subject to adhere to protocol requirements
- Disease progression
- Subject decision to withdraw from the study (withdrawal of consent)

Subjects who withdraw from the study for any reason will have their information recorded at the time of withdrawal. At the time of withdrawal, the subject will be considered at the final treatment date and will move into the treatment observation phase (4 weeks). Subjects will not be replaced. Follow up for subjects will continue to follow the normal follow up (Table-2)

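### Last observation carried forward, the only missing-data sensitivity analysis, does not test missing at random, so its agreement with the mixed model would not show robustness

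*Combined protocol and SAP*

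**What the plan says.** The primary endpoint (section 3.4) is the change in NL score of the index lesions from Week 0 to Week 12. Section 7.2 uses a mixed model for change over time if missingness is at random. The single check on it reads "A sensitivity analysis will be performed using the last observation carried forward", with the two results to be compared. No analysis is planned under data missing not at random, and no method is named for the case where the condition fails.

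Section 4.4.1 defines what happens on withdrawal: "At the time of withdrawal, the subject will be considered at the final treatment date". A 4-week observation phase follows, the Table-2 follow-up schedule is kept, and subjects are not replaced. Disease progression is one of the listed reasons for withdrawal. Section 7.3 analyses everyone who received a dose, so withdrawn subjects count in the primary result. Section 7.2 does not say whether scores taken after the cream is stopped enter either analysis, and no estimand is stated.

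Section 1.1 describes NL as a "chronic, disfiguring, relapsing-remitting inflammatory disease". The secondary outcome measures in section 3.1 treat duration of response after stopping as something to be learned.

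**The concern.** A sensitivity analysis is useful when it moves the assumption that cannot be checked. The mixed model takes withdrawn subjects to have continued like comparable subjects who stayed. Last observation carried forward (LOCF), applied to an on-cream score, takes them to have kept the level of their last visit. Neither represents a subject who improves, stops the cream and loses the gain. If that happens and no off-cream score is used, the two methods can share an error, and their agreement would be read as reassurance.

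The stake is the estimate itself. Section 7.2 states "With 12 subjects, the study is intended to be for estimation purposes only", and the effect sizes are meant to size later trials. With 12 subjects, two or three withdrawals carry a sixth to a quarter of the weight.

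**Working it through.** **Inputs from the documents.** N = 12 ("12 subjects will be enrolled in this study"), set without a calculation ("The sample size for this pilot study is set at 12 subjects for logistical and financial reasons"), so there is no plan figure to reproduce. No dropout rate is given for this trial. The only 12-week figure is from a psoriasis study of 199 participants, "161 (80.9%) completed the Day 84 visit": 1 − 161/199 = 19.1%, and 0.191 × 12 = 2.3. It is used only to motivate a range of 2 to 3 withdrawals.

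**Assumed inputs (not in the documents).** Baseline score 6; mean on-cream change at Week 12 of −3; SD 1.5 for baseline and for response; residual SD 0.6; 3 of 12 withdrawn.

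**Hand calculation for random withdrawal, full loss of response, no off-cream data.**
- Off-cream truth: (9 × −3 + 3 × 0)/12 = −2.25.
- Mixed model: about −3.00, an error of −0.75 (negative means too favourable).
- LOCF: the error is 3/12 times the gain at the last on-cream visit. The simulated LOCF means differ from the on-cream mean by 0.48, 0.30 and 0.09 for stopping after Week 2, 4 and 8. Multiplying by 12/3 gives shortfalls of 1.92, 1.20 and 0.36, so the carried gains are 1.08, 1.80 and 2.64. The errors are then 0.25 × 1.08 = 0.27, 0.25 × 1.80 = 0.45 and 0.25 × 2.64 = 0.66, all too favourable.
- With 2 of 12 withdrawn, each error is two-thirds as large.

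**Simulation.** 1,500 replicates; visits at Weeks 0, 1, 2, 3, 4, 8 and 12; an idealised mixed model with a mean for each visit and known covariance. The table gives the error against the off-cream Week 12 outcome for stopping after Week 2 / 4 / 8.

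| Who withdraws, and what follows | Mixed model | LOCF |
|---|---|---|
| Random, full loss | −0.75 / −0.74 / −0.76 | −0.27 / −0.45 / −0.67 |
| Random, half lost | −0.62 / −0.52 / −0.43 | −0.13 / −0.23 / −0.34 |
| Random, response kept | −0.48 / −0.29 / −0.09 | about 0 |
| Poor responders, full loss | −0.51 / −0.43 / −0.38 | −0.08 / −0.17 / −0.26 |
| Poor responders, response kept | −0.32 / −0.17 / −0.04 | +0.11 / +0.09 / +0.07 |
| Progression of 2 points, half of it kept | −0.09 / +0.16 / +0.13 | +0.25 at each |
| Progression of 2 points, fully resolved | +0.17 / +0.40 / +0.38 | +0.50 at each |
| Random, full loss, one off-cream score 4 weeks after stopping used | −0.35 / −0.36 / 0.00 | about 0 |

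In the first row the two methods differ by 0.48, 0.29 and 0.09. The error is therefore least visible for late withdrawals, where LOCF is also most wrong.

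**On-cream target.** With random withdrawal the mixed model is about unbiased and LOCF errs against the drug by 0.09 to 0.48. With withdrawal for progression, and the worsening assumed to continue on cream, both are too favourable (LOCF by about 0.1 to 0.9, mixed model by about 0.2 to 1.2).

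**Scale.** Under these assumptions the SD of a change is √(1.5² + 2 × 0.6²) = 1.72. The 95% half-width for 12 complete subjects is 2.201/√12 × 1.72 = 0.635 × 1.72 = 1.09. An error of 0.7 is roughly two-thirds of that.

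**The case against.** The strongest objection is that the protocol plans to collect the scores that the worst case treats as absent. A subject who stops after Week 8 reaches Week 12 inside the 4-week observation phase, and Table-2 schedules the NL score there. Using one off-cream score takes the LOCF error to about zero, provided that the off-cream level is reached by then. This largely stands: the 0.7-point illustration describes subjects lost to follow-up, subjects who withdraw consent, or off-cream scores that exist but are left out. It does not settle the matter. Section 7.2 does not say whether these scores count, and section 4.4.1 does not make clear whether visits after an early stop last 4 weeks or run to Week 12.

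Three further objections also stand. Relapsing-remitting describes the natural history of the disease; it does not show full loss within weeks of stopping. Return to baseline matches the truth in the illustration because the illustration assumes it. The psoriasis study gives no reasons for non-completion and pools four arms, one of them vehicle, so its 19% need not carry over. This trial also offers virtual visits.

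A reader might infer that LOCF and the mixed model always err together in the drug's favour once the cream is stopped. The documents do not support that. It needs an off-cream target, improved subjects who relapse, and no use of observation-phase scores. A reader might also infer that carrying an off-cream score forward adds favourable bias. In the scenarios run with the off-cream target it largely removes the LOCF bias.

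**Conclusion.** The point holds in a conditional form. LOCF does not test a departure from missing at random, and its direction of error depends on who withdraws, what happens off cream, which target is meant and which scores are used. Near-agreement can coexist with a shared error of about 0.7 points (3 of 12 withdrawn after Week 8) or about 0.5 (2 of 12). Disagreement, such as the 0.29 to 0.48 seen for earlier random withdrawal, does not show which analysis is closer to the truth.

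It would be tempting to say that the plan overstates benefit by a third (0.75/2.25). That ratio follows only from the assumed full return to baseline with no off-cream data. The possibility of a shared error is the finding; the sizes are illustrations on assumed values. The consequence is moderate: this is an estimation-only pilot, but the estimate is its product, and the correction is cheap.

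**What to change.** 1. Keep the mixed model as the main analysis.
2. State whether the Week 12 target includes scores after stopping the cream. Flag observation-phase scores as off-treatment and use or exclude them accordingly in every analysis. Reconcile the two statements on follow-up in section 4.4.1, since they decide which scores exist.
3. Replace LOCF, or demote it to a secondary check, with two analyses:
   - a return-to-baseline imputation for withdrawn subjects whose Week 12 score is missing, presented as one scenario;
   - a delta-adjusted analysis that adds a fixed range, for example 0.5 to 3 points, to imputed Week 12 scores. With 3 of 12 imputed, the mean moves by 0.25 × 0.5 = 0.125 up to 0.25 × 3 = 0.75 points. Under the assumed values the upper end, −3.00 + 0.75 = −2.25, meets the return-to-baseline result.
4. Report these as a range of estimates with intervals. A tipping point does not fit, because the study has no decision threshold to tip.

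The cost is SAP wording, a few more lines of analysis and possibly a less favourable sensitivity estimate. No extra visits or subjects are needed.

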### Bioinformatic Analysis:

RNA-seq analysis: We will use our recently developed LinNorm program

to process RNA-seq data and detect differentially expressed genes (DEGs) by comparing the RNA-seq profiles. We will first find DEG between responsive and non-responsive samples from the same individual by using paired or unpaired Wilcoxon rank-sum test (depending on how the samples are collected). We will then rank each gene in the DEGs based on the occurrence frequencies in all 12 subjects to find common DEGs for responsiveness (use permutation test to determine the p value). By comparing the normal tissue with the pathogenic tissue (responsive + non-responsive) using the above approach, we will detect a common DEGs for NL pathogenesis. Hierarchical clustering and Principal Component Analysis (PCA) will be applied to samples for their hierarchical relationship and clustering properties. Ideally normal, responsive and non-responsive tissues should form three distinct groups. The PCA analysis will provide us a set of gene signatures that can distinguish these three types of tissues. The common DEGs for responsiveness and pathogenesis, as well as gene signature from PCA will be used for our pathogenesis or survival

prediction. Additionally, we will perform de-convolutional analysis, to compare the immune profiles of responsive and non-responsive tissue and to correlate immune profiles. Predictive biomarkers will be correlated with lesional and global responses.

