Tissue will be collected for RNA sequencing at week 0 and 4. Blood collection will include the isolation at week 0, 2, 4, 8, 12. 5mL vials of blood which will be separated and the serum and cell

pellet will be stored for future analysis. Three skin biopsies will be taken during the study. At week 0, one 3mm tissue biopsy will be taken from lesional skin and one biopsy will be taken from non-lesional (adjacent but normal-appearing a minimum of 2 cm from the primary lesion but within the same anatomical subunit) skin. At week 4, a 3mm biopsy will be taken from a treated lesion (Ideally the same lesion as the initial biopsy, separated by a minimum of 1cm, or a similar lesion in the same anatomical subunit). The lesions will be chosen using full body photographs taken at week 0. From the biopsy specimen, a small piece of tissue (approximately 1 mm) will be cut and placed in a bottle labeled for RNAseq. The larger specimen will be placed in a bottle labeled for biobank storage. Both samples will be snap frozen and stored in the biobank. Once sample collection is completed for all samples, the tissues labeled for biobank storage will continue to be stored in the biobank and RNA sequencing will be performed on the tissue samples labeled for RNAseq (up to 36 tissue samples) and analysis will be performed. Paired analysis of treatment responsive and refractory lesions will be made as well as treated and untreated lesions.

**Nucleic Acid Extractions:** RNA will be extracted from a total of 50 um of fresh tissue using the Qiagen FFPE RNeasy Micro extraction Kit according to manufacturer's recommendation.

**RNA Transcriptome Sequencing:** RNA transcriptome sequencing will be carried out using commercially available techniques. Briefly, RNA libraries will be created using up to 100ng of RNA as starting material using the Illumina RNA TruSeq Library kit according to manufacturer's recommendation. Libraries will be QCed for quality and quantity using the Illumina TapeStation High Sensitivity tape. Paired-end sequencing will then be carried out on the Illumina HiSeq 4000 using 101bp insert fragments.

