**Table-2: Screening and Visits (+/- 3 day window)**

	Screening	Day 0	Week 1	Week 2	Week 3	Week 4	Week 8	Week 12	Week 16
Ruxolitinib*		X	X	X	X	X	X		
Physical Exam	X	X	X	X	X	X	X	X	X
Adverse Event Assessment		X	X	X	X	X	X	X	X
Chest X-ray	X								
Assessments: PGA, BSA, lesional number, NL Lesion, Skindex-16, Pruritus NRS		X	X	X	X	X	X	X	X
Photographer		X	X	X	X	X	X	X	X
Skin Biopsy (tissue/serum bank)		X				X			
Urine Pregnancy Test	X								
Venipuncture	X	X	X	X	X	X	X	X	X
Biomarker/RNAseq blood (tissue/serum bank)		X		X		X	X	X	
CMP	X		X	X	X	X	X	X	X
CBC	X		X	X	X	X	X	X	X
Quantiferon Gold	X								
Hepatitis B	X								
Hepatitis C	X								
HIV	X								
Coccidioidomycosis	X								

\*Patients will receive 1.5% ruxolitinib cream tubes to apply cream at home BID inbetween visits to be applied from Day 0 through Week 12. Patients will not receive 1.5% ruxolitinib cream at Week 12 visit as this begins their follow up period.

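### The within-subject responsive v non-responsive gene comparison cannot be run, because each subject supplies only one on-treatment tissue sample

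*Combined protocol and SAP*

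**What the plan says.** Section 7.2, under Bioinformatic Analysis, sets out the route to genes linked with response. The first step is: "We will first find DEG between responsive and non-responsive samples from the same individual by using paired or unpaired Wilcoxon rank-sum test". A parenthesis adds that the paired or unpaired form will follow from the way samples are collected. Genes found this way are then ranked by how many of the 12 subjects show them, with a permutation p value, to give the shared responsiveness genes. The same approach is to be used for normal v pathogenic tissue, where pathogenic means responsive and non-responsive tissue together. The two gene sets and a PCA signature then feed the prediction step.

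The tissue is described in Section 3.1: "Three skin biopsies will be taken during the study". At week 0 there is one lesional and one non-lesional biopsy; Section 6.2 confirms it ("2 tissue samples will be taken"). Then: "At week 4, a 3mm biopsy will be taken from a treated lesion". Section 6.6 lists one sample at that visit. Table-2 marks skin biopsy at Day 0 and Week 4 only, and Section 12.2 pays for biopsy visits at those two times only. From each specimen, "a small piece of tissue (approximately 1 mm) will be cut and placed in a bottle labeled for RNAseq"; the remainder goes to the biobank. The sequencing total is capped at 36 tissue samples.

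Section 3.1 also says: "Paired analysis of treatment responsive and refractory lesions will be made as well as treated and untreated lesions".

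**The concern.** A comparison of responsive with non-responsive tissue inside one person needs at least one sample of each kind from that person. Response can be judged only in tissue that has been treated, and each subject gives one such sample. Response status therefore differs between subjects but not within a subject's on-treatment tissue.

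This step is the plan's only stated differential-expression route to responsiveness, and one of three inputs to the prediction step. Section 7.1 gives biomarkers predictive of response as part of the reason for the 12-subject design. If the step cannot be run as written, the analyst has to substitute another contrast. The study is open-label, and sequencing starts only after all samples are collected, so clinical response may already be known when that choice is made. The plan also does not say which scale, or which visit, makes a tissue sample responsive.

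**Working it through.** **Inputs**

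- Subjects: 12 (Section 3.2).
- Biopsies per subject: 2 at week 0 and 1 at week 4 (Sections 3.1, 6.2, 6.6; Table-2).
- RNAseq pieces per biopsy: 1 (Section 3.1).
- Within-subject significance cutoff, sidedness, split of responders: none stated. Any value used below is an assumption.

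**Step 1. Reproduce the plan's own figures.** 12 × (2 + 1) = 36, exactly the stated maximum. As a cross-check on biopsy visits, nine visits with two paid as biopsy visits give 2 × $50 + 7 × $25 = $275, the total in Section 12.2. Both counts leave no room for a second on-treatment lesion.

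**Step 2. Count the tissue available to the contrast.** On-treatment samples: 12 × 1 = 12, one per subject. Subjects who can supply both a responsive and a non-responsive on-treatment sample: 0 of 12. The within-subject comparison is 1 v 0 and returns no result. The ranking over subjects and its permutation test have no input.

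**Step 3. Try week-0 lesional tissue as the comparator.** The smallest two-sided exact p is 2/C(n1+n2, n1), capped at 1, for the rank-sum test, and 2/2^m for the signed-rank test with m pairs.

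- 1 v 1: 2/C(2,1) = 2/2 = 1.0.
- One pair: 2/2 = 1.0.

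Every gene in every subject gives p = 1.0. The contrast is also untreated v treated tissue, so response and treatment cannot be separated.

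**Step 4. What a within-subject test would need.** At an assumed cutoff of 0.05, seven samples are not enough (3 v 4: 2/35 = 0.057). Eight are the minimum (4 v 4: 2/70 = 0.029; 3 v 5: 2/56 = 0.036), or six pairs (2/64 = 0.031). At an assumed 0.10, the minimum is six samples (3 v 3: 2/20 = 0.10) or five pairs (2/32 = 0.0625). The schedule gives one on-treatment sample.

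**Step 5. Normal v pathogenic tissue.** Run inside each subject, this is 1 v 1 (p = 1.0) or 1 v 2 (2/3 = 0.667) at best. Run as matched pairs across subjects, the smallest p is 2/2^12 = 0.00049 with 12 pairs, or 2/2^10 = 0.0020 with 10. This step is therefore ambiguous, not impossible.

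**Step 6. Responders v non-responders across subjects.** The split is not known in advance, so a range is shown. The 10-subject rows assume two losses; Section 4.4.1 allows no replacement.

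| Subjects | Split | Smallest two-sided p, per gene |
|---|---|---|
| 12 | 6 v 6 | 2/924 = 0.0022 |
| 12 | 4 v 8 | 2/495 = 0.0040 |
| 12 | 2 v 10 | 2/66 = 0.030 |
| 12 | 1 v 11 | 2/12 = 0.167 |
| 10 | 5 v 5 | 2/252 = 0.0079 |
| 10 | 2 v 8 | 2/45 = 0.044 |
| 10 | 1 v 9 | 2/10 = 0.20 |

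These values make no allowance for testing many genes. Under Bonferroni at an assumed 0.05, the best split (6 v 6) could reach significance with at most 0.05/(2/924) = 23.1, that is 23, genes tested.

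**The case against.** Several points can be made for the plan.

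- **Labels could differ within a subject.** The week-4 biopsy may come from a similar lesion, not the one sampled at week 0, and all lesions are scored. If week-0 tissue were labelled by the later outcome of its lesion, one subject could hold both labels. This is a fair qualification of the 1 v 0 count, but it only reaches the 1 v 1 case in Step 3: p = 1.0 and confounded with treatment.
- **The test family is already named.** Section 7.2 specifies paired or unpaired Wilcoxon tests, so the repair is mainly to the unit of comparison. That is right, and it keeps the repair small. The sample-collection parenthesis, however, only chooses between the paired and unpaired forms; it adds no second sample.
- **Other response analyses survive.** PCA, clustering, deconvolution and the correlation of biomarkers with response can still be done. The Section 3.1 sentence on responsive and refractory lesions can be read as week-0 v week-4 pairs within each response group, which is computable. All of this stands.
- **The study is exploratory and for estimation only.** This limits the severity. It does not rescue the step, since a contrast without a comparator estimates nothing.
- **Some proposed contrasts overlap with planned work, and the between-subject p values are per gene.** Both are true. Only the responder contrast replaces the failed step, and it should not be presented as strong.

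**Conclusion.** The concern holds. The stated within-subject responsiveness test cannot be computed on the stated biopsy schedule in any of the 12 subjects, and the frequency ranking built on it has no valid input. This rests on two readings that the documents support consistently: one RNAseq piece per biopsy, and one treated-lesion biopsy per subject. It does not depend on the assumed cutoffs, splits or losses, which only show scale.

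The damage is confined to the exploratory objective of a pilot, where it removes one of three inputs to prediction. The PCA signature remains, as do the pathogenesis genes if they are tested across subjects. It should be fixed because the substitute contrast and the responder label would otherwise be chosen with clinical response potentially known.

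There is a separate wording point. The Study Summary and the exploratory outcome in Section 3.1 place this tissue at week 12, while the exploratory objective in Section 2, the biopsy description in Section 3.1, Table-2 and Section 6.6 place it at week 4. The version history records a move from week 12 to week 4, so the week-12 text is probably left over. It is an inconsistency to tidy and adds nothing to the severity.

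**What to change.** Replace the within-subject responsive v non-responsive step with contrasts that take the subject as the unit and use the up to 36 samples already planned:

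1. Week-0 lesional v week-0 non-lesional tissue, paired across subjects, for pathogenesis. Keep treated week-4 tissue out, so that treated and untreated samples are not pooled as pathogenic.
2. Week-4 v week-0 lesional tissue, paired across subjects, for the treatment effect on expression.
3. Responders v non-responders, for both the week-4 minus week-0 change and week-0 lesional expression.

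Before expression data are examined, fix one responder definition from the scales already collected, the visit at which it is read, and the error-control level. State that the third contrast is coarse with 12 subjects, that its smallest p values are per gene, and that it will be reported as estimation. Clarify, and do not delete, the Section 3.1 sentence on responsive and refractory lesions. Reconcile the week-12 tissue wording with the week-4 biopsy.

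The cost is plan wording and standard analysis code, with no extra tissue, subjects or assays. Because the analysis plan sits inside the protocol, the change goes to the IRB as an amendment (Section 11). The documents do not show trial status; if sequencing has already been done, the change should be dated and reported as made after data collection.
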